In this repeated-measures design, each patient will be tested in a “*Control*”, or baseline condition, and a pre-determined stimulation level of “*Stochastic Vestibular Stimulation (SVS)*” up to 1mA. In the *Control* condition: the entire testing will be conducted with the system worn but without SVS application (i.e., 0mA). The patient will be instrumented with electrodes without turning on the SVS device throughout the testing. In the SVS condition: The SVS device will be active throughout the testing at the respective current level. The test will be performed for a singular, pre-determined, GVS amplitude up to 1mA. The order of the conditions will be randomized across subjects. The details of testing (single visit) are summarized below.

Equipment:

The VIPES system that provides SVS is a small wearable device in order to improve the function of an individual’s vestibular system that has been adversely affected their balance due to head injuries and mild TBI. In particular, VIPES is designed to provide electrical stimulus comprising random noise in a low frequency band (0 to 5Hz maximum) below the level of perception by the subject. The VIPES system consists of the four electrodes (two behind each ear) similar to our commercial galvanic stimulator (Good Vibrations Engineering Ltd, King City, ON; used in the previous IRB approved projects – IRB #s: 20-005763, -19-003257, 18-005564, 14-003906, 11-007718, 09-003815). The stimulator can bidirectionally deliver the electrical stimulation and receive information about the amplitude delivered accounting for skin impedance. Bertec Portable Essential’s dual-balance plate balance system (previously IRB approved in IRB 20-005763) used for balance testing is clinically used in Mayo Clinic Arizona.

Testing:

Following documentation of consent for study participation, participants will complete pre-testing questionnaires and medical history evaluations. Subjects will don the VIPES device and the research team will verify the system is set to 0mA and participants will then be given a direction and timeframe to walk in the Mayo Clinic space for up to 10 minutes before returning to the laboratory, as a means of establishing baseline gait, balance, stability, and pace to be measured by an incorporated accelerometer (sway score; deg/s). Once returned, participants will be allotted a 5-minute resting period prior to beginning the ‘*Condition*’ testing.

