Subjects will complete a series of balance tests to establish and describe a range of balance performance. The Modified Clinical Test of Sensory Interaction and Balance (mCTSIB) [4], and COBALT Balance test [5] are measures of standing balance that increase in difficulty. These metrics will be included for the rationales noted below, but also to better describe the wide ability of balance function in individuals with balance disorder.

Subjects will be randomized for balancing testing condition order and will complete the mCTSIB and COBALT with the system providing a known amount of electrical stimulus, as well as with the system providing 0mA, but will be blinded for which condition is taking place. Participants will be permitted to leave and walk normally about the premises with the VIPES system now provided the known-stimulation dose. A member of the investigational team will accompany the subjects for the duration of their walking. Subjects will return after ~30-45 mins and will be allotted an additional 5-minute resting period. Subjects will complete the mCTSIB and COBALT balance tests with the system delivering stimulation. Once completed, the VIPES system will be

removed and participants will answer the Post-Testing Questionnaires before finishing the study day and being provided remuneration. The details of testing are summarized as follows:

Visit:	Duration
Consent & Pre-Testing Questionnaire(s) 
 Post-concussion symptoms scale Demographics & Medical History 	10 mins
Baseline Walk 
 Participants will walk with the system at 0mA, as is normal, for up to 10 minutes to establish baseline gait Subject will rest for approximately 5 minutes. 	15 mins

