COBALT Balance Test: Device: Bertec Portable Essential's dual-balance plate balance system (https://www.bertec.com/bertec-balance-advantage-systems) Rationale: COBALT is a balance test commonly used to evaluate individuals post-concussion. This test protocol places high demand on the visual and vestibular systems that is not provided by traditional balance tests. These higher demand conditions improve sensitivity in detecting balance dysfunction in those post-concussion. The test will be performed for a given SVS amplitude up to 1mA and 0mA, and will be randomized for each subject. Two 20-seconds trial for each of the following conditions/surfaces: On Firm Surface: 
 Head Shake Visual Motion Sensitivity On Foam Surface: 
 Head Shake Visual Motion Sensitivity 	10 mins
Modified Clinical Test of Sensory Integration on Balance (mCTSIB): Device: Bertec Portable Essential's dual-balance plate balance system (https://www.bertec.com/bertec-balance-advantage-systems) Rationale: mCTSIB is a balance test commonly used to evaluate individuals of all ages post-concussion. This test protocol assesses how well an individual uses sensory input when one or more sensory systems are	10 mins

compromised. This protocol is commonly used to evaluate individuals post-concussion to describe static balance ability.

The test will be performed for a given SVS amplitude up to 1mA and 0mA, and will be randomized for each subject.

Three 10-second trials for each of the following conditions:

- Standard (eyes open on firm surface)
- Proprioception (eyes closed on firm surface)
- Vision (eyes open on foam surface)
- Vestibular (eye closed on foam surface)

SVS Condition Walk	50 mins
Repeat mCTSIB and COBALT	20 mins
Post-testing Questionnaires:	5 mins

Subject Information

Target accrual is the proposed total number of subjects to be included in this study at Mayo Clinic. A “Subject” may include medical records, images, or specimens generated at Mayo Clinic and/or received from external sources.

Target accrual: 40 participants

Subject population (adults, groups): Patients – 1) diagnosed with a balance disorder and/or having sustained a concussion and/or mild traumatic brain injury (mTBI), 2) Currently being evaluated at Mayo Clinic Arizona, 3) self-reported imbalance,

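### The post-walk balance tests are SVS-only and always last, yet the planned ANOVA read literally pools them into the SVS level, adding half of any order shift to the SVS minus 0 mA contrast

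*Combined protocol and SAP*

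**What the plan says.** **Conditions.** The Protocol paragraph under Study Design and Methods defines two conditions. For Control, "the entire testing will be conducted with the system worn but without SVS application (i.e., 0mA"). For SVS, the device is on throughout. There is one active level: "The test will be performed for a singular, pre-determined, GVS amplitude up to 1mA". It adds: "The order of the conditions will be randomized across subjects".

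**First block.** The Testing text has each participant do both balance tests with stimulation and at 0 mA. "Subjects will be randomized for balancing testing condition order", it says, "but will be blinded for which condition is taking place". The visit-table rows for COBALT and mCTSIB agree: "The test will be performed for a given SVS amplitude up to 1mA and 0mA, and will be randomized for each subject".

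**Walk and repeat block.** Next, "Participants will be permitted to leave and walk normally about the premises with the VIPES system now provided the known-stimulation dose". After about 30-45 minutes and a 5-minute rest, "Subjects will complete the mCTSIB and COBALT balance tests with the system delivering stimulation". The device then comes off. The text describes no post-walk test at 0 mA, and it states no randomisation or blinding for this block. The visit table's repeat row names no condition and allots 20 minutes, the same total as the two first-block rows (10 + 10).

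**Analysis.** The Data Analysis Plan is a repeated measures ANOVA of sway score, with stimulation amplitude versus control as its only named factor. It does not mention the repeat block, a period term or a planned contrast. The primary endpoint describes what the device will deliver and names no variable, block or comparison.

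**The concern.** Each participant gives three sets of balance measurements: 0 mA and SVS in random order, then SVS again. The first two form a randomised comparison. The third has no concurrent control and always comes last.

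Both SVS runs use the same amplitude, so a factor defined only by amplitude puts them in one level. The 0 mA mean then comes only from the first two positions, while half of the SVS mean comes from the third. Any net improvement by the third position would be credited to stimulation, and any net worsening would hide part of a real effect. The study already collects a comparison free of this problem, but the plan does not commit to using it.

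**Working it through.** **1. The plan's own figure.** The Power Statement gives 22 participants, 80% power, two-sided 5%, and targets of 0.08 (firm) and 0.17 (foam). It calls these standardised but also gives them in deg/s. A paired t-test at n=22 has 80% power when effect/SD of the difference is 0.6264.
- Read as standardised differences, the targets have power 6.5% and 11.9% at n=22, so the figure does not reproduce.
- Read as deg/s, it reproduces only if the SD of the difference is 0.08/0.6264 = 0.128 (firm) and 0.17/0.6264 = 0.271 (foam). The documents give no SD.

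The sample-size question is separate. These SDs serve below only to set a scale.

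**2. Bias of the pooled contrast (no SD needed).** Let m be the average level of the first two positions, E the SVS effect, and D the last-block shift from m, with order balanced.
- 0 mA run: m. First SVS run: m + E. Repeat SVS run: m + D + E.
- Pooled SVS minus 0 mA: [(m + E) + (m + D + E)]/2 - m = E + D/2.

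A shift of half the target (0.04 firm, 0.085 foam) moves the estimate by 0.02 and 0.0425 deg/s.

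**3. Type I error if pooled (illustrative).** Assumptions: SDs as in step 1, equal independent errors per run, no person-to-person variation in the SVS effect, 11 participants per order, and no change between the first two positions. Write T for the target.
- With error variance s² per run, SD² = 2s². The pooled contrast has variance s²(1 + 1/2) = 0.75 SD².
- Noncentrality = √22 × (D/2)/(SD × √0.75). It is 0.42, 0.85 and 1.70 at D = 0.25T, 0.5T and T.

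| Improvement D, no SVS effect | Pooled paired test | Two-level ANOVA on three rows per person (simulated) |
|---|---|---|
| 0.25T | 6.9% | 6.8% |
| 0.5T | 12.8% | 12.3% |
| T | 36.7% | 30.6% |

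A larger sample does not help: at n=30 the pooled paired test gives 8%, 16% and 48%. Both surfaces give the same rates because D is scaled to T.

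**4. Opposite sign.** With a true effect T and worsening of 0.25T, 0.5T and T, pooled power is 81-82%, 68% and 31-37%, against 80% for the first block. Pooling loses power once 1 - d/2 < √0.75, that is, once worsening exceeds d = 0.27 of T.

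**5. What the first block delivers.** If SVS leaves a residual effect c on a 0 mA test that follows it, half the participants carry it and the contrast becomes E - c/2. A period term does not remove this. Power is then about 69% at c = 0.25T and 56% at c = 0.5T (c is assumed). With no SVS effect there is nothing to carry over, so the test of no effect is protected.

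**6. What is given up.** With D = 0, pooling would have about 90% power against 80%. Its mean squared error is smaller when D²/4 < 0.25 SD²/22, that is, D < SD/√22 = 0.34T (0.027 deg/s firm, 0.058 foam).

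**The case against.** The best defence is that the plan already points to SVS versus 0 mA. The protocol defines two conditions, the Data Analysis Plan speaks of a difference between two means, and the stated aim is immediate improvement. That is fair, and it makes a comparison of the two conditions the natural reading. It does not say which SVS runs supply the SVS mean, and the factor as written takes both.

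A reader might go further and infer far larger error rates. Comparing the repeat run alone with 0 mA would give 11%, 29% and 80% at the three values of D. An overall F test with the repeat as a third level would give 10%, 29% and 84%. The documents do not support either inference: nothing suggests discarding the first SVS run, and the named factor has two levels.

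Three further points stand. D may be small, and pooling would then be the more precise choice. Comparing repeat SVS with first-block SVS could check the shift, but weakly: its standard error equals that of the efficacy contrast, so it detects a shift of 0.5T only about 29% of the time, and it cannot split order effects from sustained stimulation. Finally, that the repeat is SVS-only rests on the Testing text. The visit table's 20 minutes would also fit a two-condition repeat, though the Testing text is the more explicit of the two.

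**Conclusion.** The concern holds as a fault in the analysis plan that should be fixed. Followed literally, the plan puts a non-randomised, always-last SVS run into the SVS level and biases SVS minus 0 mA by D/2. That result needs only balanced order and the literal reading of the factor. The error rates rest on back-solved SDs, equal independent errors and assumed values of D, and are illustrations.

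Two stronger conclusions might be drawn and are not supported. The documents do not show that the result will be biased, since neither the size nor the sign of D is known and the plan does not explicitly say the runs will be pooled. Nor does the study lack a sound efficacy test: the first-block contrast is randomised and blinded, and it tests the null validly. It is an unbiased estimate of the effect only if SVS does not carry over to a following 0 mA test, and the documents state no washout between the two conditions.

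**What to change.** In the analysis plan:
1. Name SVS versus 0 mA from the randomised, blinded first block, with a period term, as the efficacy contrast. When order is balanced, the term is there for correct error bars and efficiency: with a change of 0.05 deg/s between the first two positions and SD 0.128, type I error is 3.6% and power about 75% without it, against 5% and 80% with it. The documents promise random order, not balance; an 8:14 split would leave 6/22 = 0.27 of that change in the contrast without the term.
2. Analyse the post-walk SVS block separately, as exploratory, and do not pool it into the condition effect.
3. State that the first-block contrast tests the null validly but is an unbiased estimate only without SVS-to-0 mA carryover.
4. Reconcile the Protocol paragraph (all testing under each condition, randomised order) and the visit table's repeat row with the Testing text.

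Visits and tests need not change for items 1-3. The cost is a few sentences, one degree of freedom for the period term, the precision of the second SVS measurement, and exploratory status for the post-walk result.

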- The study plans to include subjects previously diagnosed with a specific disease and add newly diagnosed subjects in the future.

The study will use data that have been collected under another IRB protocol. Include in the Methods section and enter the IRB number from which the research material will be obtained. *When appropriate, note when subjects have provided consent for future use of their data and/or specimens as described in this protocol.*

Enter one IRB number per line, add more lines as needed

Data Specimens Data & Specimens _____

Data Specimens Data & Specimens _____

Data Specimens Data & Specimens _____

Data Analysis

Power analyses may not be appropriate if this is a feasibility or pilot study, but end-point analysis plans are always appropriate even if only exploratory. Provide all information requested below, or provide justification if not including all of the information.

Data Analysis Plan:

We will use repeated measures ANOVA to examine changes in balance performance during balance testing by measuring sway score (i.e., sway angular velocity, deg/s) across tested levels of GVR amplitude and control condition. Sample size estimates are based on: (1) the expected variability (s^2) in the response parameters, (2) the alpha (α , type I) error level, or probability of incorrectly concluding there is an effect when responses are equivalent, (3) the magnitude of the effects to be detected between the means (μ_1, μ_2), and (4) the certainty (statistical power, $1 - \beta$) with which the effect is to be detected. Sample sizes can be calculated based on the expected standardized differences (Δ) between conditions.

Power Statement:

Standardized mean differences of 0.08 deg/s on firm surface and 0.17 deg/s on foam surface will be considered operationally relevant effect sizes for balance performance comparison based on previous balance testing protocols using the COBALT testing [5]. Based on the equation above, we will have 80% statistical power to detect standardized mean differences (two-sided tests) of 0.08 (firm surface) and 0.17 (foam surface) with an

alpha error level of 0.05 with a sample of 22 participants. A target of at least 30 participants is requested to account for incomplete data sets.

Endpoints

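### The power statement gives 0.08 and 0.17 both as standardized differences and in deg/s; 80% power with 22 participants fails on the first reading and cannot be checked on the second

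*Combined protocol and SAP*

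**What the plan says.** The outcome is the sway score. The Data Analysis Plan defines its unit when it describes "measuring sway score (i.e., sway angular velocity, deg/s) across tested levels" of stimulation. The same paragraph names variability as a sample-size input: "Sample size estimates are based on: (1) the expected variability (s^2) in the response parameters". It then says that sample size follows from standardized differences between conditions.

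The Power Statement sets the target effects: "Standardized mean differences of 0.08 deg/s on firm surface and 0.17 deg/s on foam surface will be considered operationally relevant effect sizes", citing earlier COBALT work. The next sentence repeats the numbers without a unit: "we will have 80% statistical power to detect standardized mean differences (two-sided tests) of 0.08 (firm surface) and 0.17 (foam surface". It completes the claim with "alpha error level of 0.05 with a sample of 22 participants". An allowance follows: "A target of at least 30 participants is requested to account for incomplete data sets". The Subject Information section has "Target accrual: 40 participants".

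On design, the Protocol part of Study Design and Methods tests each patient at 0 mA and at one stimulation level, in random order: "The test will be performed for a singular, pre-determined, GVS amplitude up to 1mA".

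The Power Statement refers to an equation above it. No equation appears in the text available to us. It may have been lost when the PDF was read, and it is not counted as missing here.

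**The concern.** A standardized mean difference is a raw difference divided by an SD, so it carries no unit. The Power Statement uses the word *standardized* in both sentences and attaches deg/s in the first. The two readings lead to very different conclusions. Standardized effects of 0.08 and 0.17 are very small, and 22 participants would not normally detect them. Raw differences of 0.08 and 0.17 deg/s could be large or small, depending on an SD that the available text does not give.

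The claim also attaches one sample size and one power figure to two effects that differ by a factor of about two. That is impossible on a common standardized scale with common assumptions.

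The figure of 22, and the request for at least 30 built on it, rest on this sentence alone. If it cannot be reproduced, nobody can say which difference the study is able to detect. A null result could then not be judged against the differences that the plan calls relevant.

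**Working it through.** **Inputs.** From the Power Statement: effects 0.08 (firm) and 0.17 (foam), n = 22, two-sided alpha 0.05, claimed power 80%. The allowance of 30 is from the same section and the accrual target of 40 is from Subject Information. No SD or within-patient correlation is stated in the available text.

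**Method.** With one stimulation level against 0 mA and one score per condition and surface, repeated-measures ANOVA is equivalent to a paired t-test. Let dz be the mean difference divided by the SD of the within-patient difference. Power is the probability that a noncentral t, with n − 1 degrees of freedom and noncentrality dz × √n, exceeds the two-sided 5% critical value in absolute size.

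**1. Attempt to reproduce 80%, values taken as dz.** At n = 22 the noncentrality is 0.08 × √22 = 0.375 (firm) and 0.17 × √22 = 0.797 (foam), against a critical value of 2.080.

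| Complete participants | Power, 0.08 firm | Power, 0.17 foam | dz detectable with 80% power |
|---|---|---|---|
| 22 | 6.5% | 11.9% | 0.626 |
| 30 | 7.1% | 14.7% | 0.529 |
| 40 | 7.8% | 18.2% | 0.454 |

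The 80% is not reproduced. It would need 1,229 participants (firm) and 274 (foam). The normal approximation, ((1.960 + 0.842)/dz)², gives 1,227 and 272. The effect detectable at n = 22 is 0.626/0.08 = 7.8 times the firm value and 0.626/0.17 = 3.7 times the foam value.

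**2. Values standardized by the between-patient SD.** Then dz = d/√(2(1 − ρ)), where ρ is the within-patient correlation, assumed here. Power at n = 22:

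| Assumed ρ | Firm | Foam |
|---|---|---|
| 0.5 | 6.5% | 11.9% |
| 0.9 | 12.6% | 39.8% |
| 0.95 | 20.5% | 67.2% |

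Solving for 80% gives ρ = 1 − (d/0.626)²/2, which is 0.992 (firm) and 0.963 (foam).

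**3. One n for two effects.** On a common standardizer, the required n is in the ratio (0.17/0.08)² = 4.5. One sample size cannot give 80% for both.

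**4. Other readings tried.**
- One-sided test at 0.05: 10.0% and 19.1%.
- Values as Cohen's f, two levels: 11.1% and 33.1% at ρ = 0.5; 36.0% and 92.5% at ρ = 0.9.
- Trials wrongly counted as independent (12 per patient, so 264 observations): 25.4% and 78.6%.

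None gives 80% for both surfaces under shared assumptions.

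**5. Values as raw deg/s.** The largest SD of the within-patient difference that still gives 80% power is the raw difference divided by the detectable dz; at n = 22, 0.08/0.626 = 0.128 and 0.17/0.626 = 0.271.

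| Complete participants | Firm ceiling (deg/s) | Foam ceiling (deg/s) |
|---|---|---|
| 22 | 0.128 | 0.271 |
| 30 | 0.151 | 0.321 |
| 40 | 0.176 | 0.374 |

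One n serves both surfaces when the foam SD is 0.17/0.08 = 2.1 times the firm SD.

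The true SDs are unknown. For illustration, suppose they exceed the n = 22 ceilings by the percentages below. Power is then the same on both surfaces:

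| SD above the n = 22 ceiling | 22 complete | 30 complete | 40 complete |
|---|---|---|---|
| 25% | 61% | 76% | 87% |
| 50% | 46% | 60% | 73% |
| 100% | 29% | 38% | 49% |

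**The case against.** The strongest reply is that raw deg/s was meant and *standardized* is a stray word. The first sentence carries the outcome's own unit. Step 3 supports this: one n cannot serve both values on a common standardized scale, but it can for raw differences with a larger SD on foam. On that view the 6.5% and 11.9% describe a reading that nobody intended, no arithmetic error is shown, and what remains is a mislabelled unit. This stands as far as it goes. The low powers should be read as a test of the literal wording, not as an estimate of the trial's power. But *standardized* appears in both power sentences and in the line that leads into them, and the raw reading depends entirely on an SD that the reader cannot see.

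Second, the equation, and perhaps an SD, may have been lost in text extraction. That is possible, and no absence is charged to the plan for it. An equation would still not reconcile a standardized difference with a unit of deg/s.

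Third, both enrolment figures exceed 22, which gives some margin. On the raw reading, 40 complete participants keep power above 80% even if the SD is 25% over the n = 22 ceiling. That is fair, but the 80% claim is made for 22, and the extra participants in the request for 30 are there to cover incomplete data.

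Last, the protocol form allows power analyses to be omitted for pilot work. This protocol does not call itself a pilot, and it makes an explicit 80% claim.

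**Conclusion.** The concern holds. As literally worded, the claim is wrong by a wide margin: 6.5% and 11.9% power in place of 80%, when standardized by the SD of the within-patient difference. With the between-patient SD, 80% would need correlations of about 0.992 and 0.963, which the available text does not state. As raw deg/s, the claim may be true, but it cannot be verified without the SD for each surface.

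These results assume a paired two-sided test at 0.05 of one stimulation level against 0 mA, with one summary score per condition and surface. Confidence is high that the statement mixes scales and fails as written. No conclusion is drawn about true power on the raw reading, and the trial is not shown to be underpowered. Because the sample size rests on this statement alone, it must be corrected.

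**What to change.** State which scale applies.

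- **If raw deg/s:** delete *standardized*, give the SD of the within-patient difference (stimulation minus 0 mA) for each surface with its source, and recompute power for 22 complete participants.
- **If standardized, or if no SD can be supported:** withdraw the 80% claim for 0.08 and 0.17 and write, for example: *With 22 complete participants, a paired two-sided test at 0.05 has 80% power for a within-patient difference of 0.63 SD of the difference (0.53 if 30 are complete, 0.45 if 40 are complete).*
- **If the equation that the statement refers to already fixes the standardizer or the SD:** repeat that input beside the claim.

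The cost is a rewording and, where available, one sourced SD per surface. No extra patients are needed and the design does not change. The drawback is that the stated sensitivity may become less favourable.

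### Incomplete data sets are expected, but repeated measures ANOVA is the only method named; a mixed model fitted separately by surface on the randomized block would use the partial data, for a modest gain

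*Combined protocol and SAP*

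**What the plan says.** The Data Analysis Plan states: "We will use repeated measures ANOVA to examine changes in balance performance during balance testing". The outcome is the sway score, compared "across tested levels of GVR amplitude and control condition". No surface, task or order term is named, and no missing-data rule is given.

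The Power Statement claims 80% power at two-sided 0.05 with 22 participants, separately for firm (0.08) and foam (0.17). It then adds: "A target of at least 30 participants is requested to account for incomplete data sets". No expected rate of incomplete data is given. Subject Information puts target accrual at 40.

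Under Testing, the first balance block is randomized: "Subjects will be randomized for balancing testing condition order". After the long walk there is a second block: "Subjects will complete the mCTSIB and COBALT balance tests with the system delivering stimulation". That block has no 0 mA counterpart.

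The visit table lists four COBALT tasks, two per surface, introduced by "Two 20-seconds trial for each of the following conditions/surfaces". It also lists four mCTSIB tasks, two per surface, with three trials each.

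**The concern.** The plan expects incomplete participants and answers only with numbers. It does not say what happens to the data those participants do provide. Repeated measures ANOVA over several within-person cells, as commonly run, needs every cell filled. A participant who completes all tasks but one would then be left out of the whole analysis, and the result would rest on completers.

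Partial loss is plausible here. Participants report imbalance, and the COBALT tasks were chosen because they are demanding. Since the cells are not defined, it is open how many participants would be dropped and whether a foam failure would also remove that person's firm data. At stake is precision from data already collected.

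The plan also does not say whether the post-walk repeat enters the ANOVA. If it did, the stimulation contrast would absorb time, practice and fatigue.

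**Working it through.** **1. The plan's own figure.** For a paired comparison, n = ((1.960 + 0.842)/d)². Reading 0.08 and 0.17 as standardized paired differences gives 1,227 and 272 (1,229 and 274 with the exact t distribution). At n = 22, power is 6.5% and 11.9%. So 22 is not reproduced on that reading. The equation the Power Statement refers to is absent from the extracted text, and no SD is given.

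Working backwards, 22 participants give 80% power for a standardized paired difference of 0.626. If 0.08 and 0.17 are raw deg/s, the implied SDs of the paired difference are 0.08/0.626 = 0.128 (firm) and 0.17/0.626 = 0.271 (foam). These SDs are derived, not stated in the documents.

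**2. Over-enrolment.** 1 − 22/30 = 26.7%, so 22 complete participants remain if up to 8 of 30 are incomplete. With 40, 1 − 22/40 = 45.0%.

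**3. Gain from using partial data.** The documents give no variances or missingness rate, so these are assumed:
- 22 complete and 8 incomplete participants, with one-condition losses split evenly between SVS and 0 mA.
- One model per surface: fixed effects for task, stimulation and order; random effects for participant, participant-by-condition and participant-by-task.
- Four variance sets (participant, participant-by-condition, participant-by-task, residual): (0.5, 0.05, 0.1, 0.35), (0.4, 0, 0.2, 0.4), (0.5, 0.1, 0.2, 0.2), (0.3, 0.1, 0.1, 0.5).
- Two tasks per surface (COBALT alone) or four (COBALT and mCTSIB).

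The variance of the stimulation effect comes from (Σ X′V⁻¹X)⁻¹. Effective n is 22 times the ratio of the variance with 22 completers to the variance with all data. The SE reduction is 1 − √(22/effective n).

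| Loss in the 8 incomplete participants | Effective n | SE reduction |
|---|---|---|
| One task, under one or both conditions | 26.0-29.4 | 8.0-13.5% |
| A whole condition within the surface | 22.7-24.0 | 1.6-4.3% |
| Left before balance testing | 22 | 0% |

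For a single averaged score with within-person correlation ρ and no order term, effective n = 22 + 8(1 − ρ)/2. This is 24.0 at ρ = 0.5 (4.3%) and 22.4 at ρ = 0.9 (0.9%). Across the other structures tried for whole-condition loss the range was 0.7-4.7%; a correlation as low as 0.3 would give 24.8 (5.8%). Variances are treated as known, so all these gains are upper limits. If 22 did give 80% power, 26.0-29.4 would mean about 87-91%, and 22.7-24.0 about 81-84%.

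**4. Why one variance must not serve both surfaces.** With the SDs from step 1, the pooled SD is √((0.128² + 0.271²)/2) = 0.212. That is 1.66 times the firm SD and 0.78 times the foam SD. With 42 degrees of freedom the critical t is 2.02.
- Foam: 2.02 × 0.782 = 1.58, a two-sided normal tail of about 11%.
- Firm: 2.02 × 1.656 = 3.34 against a signal of 0.08 × √22/0.128 = 2.93, so power is about P(Z > 0.41) = 34%.

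Simulation gives about 12% foam type I error and about 36% firm power at n = 22. Separate analyses by surface hold 5% and 80%.

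**5. The post-walk repeat.** Pooled with equal trial counts, it carries half the weight of the SVS mean. An assumed session shift of 0.08 deg/s would move the contrast by 0.04, half the firm difference.

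**The case against.** The strongest reply is that the plan can be read as a simple paired comparison. Each participant has one amplitude and 0 mA, stimulation is the only factor, and power is stated per surface. On an averaged or per-task score, a mixed model then adds only the small whole-condition gain. This stands: the 8-13.5% figure needs a multi-task ANOVA with casewise deletion, which the plan does not state.

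Partial loss is also limited by design. There is a single visit, people unable to complete testing are excluded, and two or three trials per task mean that one failed trial need not empty a cell. This stands in part; the plan itself still expects incomplete data sets.

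Separate firm and foam effects do not need a mixed model. A stimulation-by-surface ANOVA or two paired analyses would give them, and analysing the surfaces separately already keeps firm data after a foam failure. This stands.

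Finally, tasks aborted because of imbalance are where missing-at-random is weakest. That is true, but completers-only analysis has the same weakness, so it does not favour leaving the plan as it is.

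**Conclusion.** The point holds as a low-cost improvement with a modest benefit. The plan expects incomplete data and names a method that, if run over several tasks with casewise deletion, would leave valid trials unused. The size depends on the pattern of loss and on assumed variances: largest when single tasks fail, small when a whole condition is lost, nil when the participant leaves before balance testing.

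A reader might infer more than the documents support:
- **That participants will be dropped, or firm data lost to foam failures.** The plan states neither a deletion rule nor the cells.
- **That the planned 22 is in danger.** It is protected up to 8 incomplete of 30. Random loss of 5% of cells would leave 30 × 0.95⁸ = 19.9 participants with all eight COBALT cells, but no such rate is given.
- **That a mixed model removes bias from failed tasks.** It does not if failure depends on sway that was never recorded.
- **That the change rescues the power claim.** It does not: 22 still does not follow from 0.08 and 0.17 read as standardized.

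The warning against a common variance rests on the raw deg/s reading, which cannot be confirmed from the documents.

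**What to change.** In the Data Analysis Plan, for the randomized SVS versus 0 mA block:

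- Fit a REML linear mixed model separately for firm and foam, or one model with surface-specific participant-by-condition and residual variances. Do not use a single variance for both surfaces.
- Include fixed effects for stimulation, task and order, and random effects for participant, participant-by-condition and participant-by-task. Average repeat trials within a participant-task-condition cell, and use small-sample degrees of freedom such as Kenward-Roger.
- Name the task set: COBALT alone, or COBALT and mCTSIB.
- Keep the post-walk stimulation-only repeat out of this contrast.
- State the missing-at-random assumption and report failed or aborted trials by stimulation condition and task. A sensitivity analysis for failures related to unrecorded sway would be a reasonable addition.
- Minor: reconcile the target of at least 30 in the Power Statement with 40 in Subject Information, and give the assumed rate of incomplete data.

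The cost is plan wording, slightly more modelling, a tally of failed trials and reliance on missing-at-random. No extra participants or visits are needed.
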